### 5.3. Significance level

#### CIP chapter 11.3 Level of significance and the power of the study

The global significance level is of the 1-sided hypothesis is 2.5%.

*A statistical power of the final analysis of 80% was used for sample size calculation.*

### 5.4. Missing Data

#### CIP chapter 11.11 Handling of missing, unused and spurious data

*Missing data: With respect to the primary hypothesis, drop-outs are considered as censored data and must not be imputed.*

*Unused data: Data not needed for pre-specified inferential analyzes are minimized and limited to baseline information which can be obtained without any additional burden for the patient. Such data could be used for descriptive and exploratory analyses.*

*Spurious data are clarified via the query management, i.e. corrected after approval of an investigator. Outliers are identified during the blind review of the data. In case of a clear evidence of a measurement error, the SAP will be updated before breaking the blind in order to avoid any bias.*

### 5.5. Exclusion of data from confirmatory data analysis

#### CIP chapter 11.1.2 Full Analysis set based on the ITT principle

*... the following patients will be excluded from the analysis set*

- *Patients of the BioMonitor group and control group in case of a drop-out before discharge from the index hospitalization*
- *Patients without signed informed consent form*

Details are presented in chapter 7.

1st Interim analyses of the primary endpoint (NOTE: Not relevant for the final analysis)

During the course of the study, data may be entered in the CDMS without instantaneous confirmation of the investigator, monitor, or data manager. In any CDMS data export there are record status information for each electronic CRF.

record_status	record_status_text
1	Completed form
2	New form
3	Open issue(s)
1147	Signed by investigator
1148	Monitor check in progress, form locked
1149	Approved by monitor
1150	Ready for analysis and locked
1151	Open query
1152	Answered query
1195	Adjudication entered

For the final analysis, all CRFs shall have the status "ready for analysis and locked" or "Adjudication entered" but for the interim analysis some other record\_status values are sufficient as described in the table below. All other CRFs will be excluded from confirmatory data analysis for the interim analysis.

Close before the 1st the interim analysis all investigational sites will be intensively monitored to check AE reporting, either to identify AEs which might be classified as primary endpoints or to confirm event-free survival. For obvious reasons, this cannot be done on the same day in all investigational sites. To avoid any bias due to non-monitored data, clinical data occurred after the start date 14JAN2020 of this monitoring phase will be excluded from confirmatory data analysis for the interim analysis.

CRFs	Sufficient record_status	Sufficient dates	Reason
enrollment	1149, 1150, 1152	Any date ≤ start of the monitoring window for the interim analysis	Monitor check of patient informed consent needed
study_termination	1149, 1150, 1152	Any date ≤ start of the monitoring window for the interim analysis	Monitor check of correct termination date needed
discharge adverse_events general_notification arrhythmia_notification who_five_well_being_index eg_5d_5l_questionnaire	1147, 1148, 1149, 1150, 1152	Any date ≤ start of the monitoring window for the interim analysis	Monitor check of clinical data is not needed but event-free survival can be confirmed until the start of the monitoring phase only.
baseline	all	Any date ≤ start of the monitoring window for the interim analysis	Randomization result is filled in automatically
eaec_adjudication 	all	all	Quality check via 2-of-3 decisions

 As the investigators have a 14 days period allowed to report Adverse Events, and in reported Adverse Events the querying process and the securing of required documentation for the EAEC takes time, it is not guaranteed that Monitors will not have to return the sites after this „final“ day. However, Adverse Events that had an onset after this day will not be used in the analysis.

## 5.6. Subgroups

### CIP chapter 11.9 Specification of subgroups

*Subgroups are predefined for exploratory analyses with respect to*

- *the occurrence of the predefined arrhythmias, and to*
- *the primary endpoint and other predefined outcomes.*

All subgroup analyses which are not pre-specified in the chapters 8 or following will be performed as ad-hoc analyses if needed.

### CIP chapter 11.9 Specification of subgroups

*The following subgroups are predefined according to their presentation at enrollment:*

- *All individual components of the CHADS2-score except the age-variable*
- *Age < median vs. ≥ median*
- *"Early enrollment" within 40 days of most recent MI vs. "late enrollment" after more than 40 days*
- *Men vs. women*
- *CHA2DS2-VASc-score ≤ 4 in men / ≤ 5 in women vs. ≥ 5 in men / ≥ 6 in women*
- *LVEF < median vs. ≥ median*
- *BMI: < 30 vs. BMI ≥ 30*
- *History of AF yes vs. no*
- *NSTEMI vs. STEMI*
- *History or presence of kidney failure yes vs. no*

The subgroup "history of AF" defined in the CIP will not be considered for subgroup analyses. This variable is missing in the Baseline CRF because patients with history of atrial fibrillation and a CHADS-VASc score as required by the CIP are indicated to receive oral anticoagulation, which is an exclusion criterion. Thus, patients with history of AF are eligible for the study only in exceptional cases and their number is insufficient for subgroup analyses.

Subgroups CHADS2

[figure not shown]
Subgroups with respect to all individual components of the CHADS2 score except the age variable, which is grouped according to the median.

Data file: Identifier patient_display_id_full	Notes	Variable name	Variable label	Variable level	Nominal values
data_SAR	descr.	subgroups_chads2_c_SAR 	Subgroups Congestive Heart Failure	nominal	0 / 1
data_SAR	descr.	subgroups_chads2_h_SAR 	Subgroups hypertension	nominal	0 / 1
data_SAR	descr.	subgroups_chads2_d_SAR 	Subgroups diabetes mellitus	nominal	0 / 1
data_SAR	descr.	subgroups_chads2_s_SAR 	Subgroups stroke or TIA or systematic thromboembolic event	nominal	0 / 1

Subgroups other

Median cut-offs are based on the ITT analysis set.

Data file: Identifier patient_display_id_full	Notes	Variable name	Variable label	Variable level	Nominal values
data_SAR	descr.	subgroups_age_ge_median_SAR 	Subgroups age < median (0) vs ≥ median (1)	nominal	0 / 1
data_SAR	descr.	subgroups_mi_enr_ge_41d_SAR 	Subgroups enrollment after most recent MI < 41days (0) vs ≥ 41 days (1)	nominal	0 / 1
data_SAR	descr.	subgroups_gender_SAR 	Subgroups gender men (0) vs women (1)	nominal	0 / 1
data_SAR	descr.	subgroups_cha2ds2vasc_SAR 	subgroups CHA2DS2-VASC low (0) vs high (1)	nominal	0 / 1
data_SAR	descr.	subgroups_lvef_ge_median_SAR 	Subgroups LVEF < median (0) vs ≥ median (1)	nominal	0 / 1
baseline	descr.	subgroups_bmi_ge_30_SAR 	Subgroups BMI < median (0) vs ≥ median (1)	nominal	0 / 1
data_SAR	descr.	subgroups_stemi_SAR 	Subgroups kind of MI NSTEMI (0) vs STEMI (1)	nominal	0 / 1
data_SAR	descr.	subgroups_kidney_failure_SAR 	Subgroups kidney failure no (0) vs yes (1)	nominal	0 / 1

## 5.7. Phase1: Event rate check (NOTE: Not relevant for the final analysis)

### CIP chapter 8.1 General considerations

... The study is operatively divided into 2 phases. In the first phase 640 patients will be enrolled within approximately 2 years after FPI. After 600 patient years of cumulative follow-up have been collected, a blinded analysis will be performed to assess the primary endpoint rate. Based on the assessed rate (see section 11.7), the study will enter the second phase or be discontinued prematurely.

...

### CIP chapter 11.7 Termination Criteria

There is a blinded evaluation of the MACE rates after the event-check, which is no interim analysis because no therapy effect is investigated. If the total number of patients with at least one MACE in both groups is less than 20 patients per 600 patient-years at the end of the event-check phase, the study will be terminated.

...

Via the Study News report, Issue 15 from June 2018, the investigators were informed that the gateway to study phase 2 has been reached. The EAEC Board evaluated 20 events as primary endpoint-related. Thus, phase 2 for the study was announced.

## 5.8. Phase2: Interim analyses (NOTE: Not relevant for the final analysis)

### CIP chapter 8.1 General considerations

In the second phase enrollment will continue in the same way, but in more investigational sites than the first phase, and without interception until up to 2900 patients entered the study.

...

The first and second interim analysis will be performed after 124 and 248 primary endpoints, respectively. Within the interim analyses the primary hypothesis will be tested based on the ITT analysis set. Additionally, the stratified randomization procedure will be checked whether there are severe deviations between the BioMonitor and the control group which indicate a failure of the randomization procedure.

No Clinical Investigation Report will be generated. Any person involved in this analysis is obliged to keep all information confidential. The Statistical Analysis Report will be delivered to the DSMB only. The DSMB will inform the steering committee and the sponsor whether to continue the study without any amendments, continue the study with an amendment (e.g. change of the sample size based on the adaptive design), or stop the study for proven superiority according to the O'Brien-Fleming design. The DSMB is also responsible to give recommendations for stopping the study for safety reasons or for futility, if applicable.

No other analyses will be conducted for the Statistical Analysis Report which is submitted to the DSMB. Only in case the DSMB recommends the discontinuation of the study, and the Sponsor decides to follow this recommendation, the further procedures will be identical to those specified for the final analysis.

## 5.9. Phase2: Final analysis

### CIP chapter 11.2 Sample Size

The original planning assumed that 372 primary events would be required to accept the primary alternative hypothesis with 80% statistical power given an assumed hazard ratio in the population of 0.7452, and the study was to be terminated after this number of endpoints had been collected.

Instead, it was decided to enter the termination phase without any avoidable further delay. Therefore, the intended number of endpoints may not be reached.

After closing the CDMS all analyses specified in this Statistical Analysis Plan have to be performed and a Statistical Analysis Report and a Clinical Investigation Report will be generated.

## 5.10. Analysis software

All analyses are conducted using SAS Version 9.4 for Windows or higher version (SAS Institute Inc., Cary, NC, USA) statistical software.

## 6. Randomization & specific Study Dates

### 6.1. Randomization

Data file: Identifier patient_display_id_full	Variable name	Variable label	Variable level	Nominal values
Baseline	randassign	Randomization result	nominal	Control (no implant) / Implant
data_SAR	rando_SAR 	Randomization	nominal	Control / Implant

### 6.2. Enrollment date

#### CIP chapter 8.9.5 Point of enrollment and study termination

*The point of enrollment is the time at which a patient signs and dates the informed consent form ... Study related procedures, documentation and collection/following of adverse events will start from this day on.*

Data file: Identifier patient_display_id_full	Variable name	Variable label	Variable level	Nominal values
enrollment	ic_date	Date of informed consent (= date of enrollment)	date	n.a.

### 6.3. Initial and latest implantation date

Data file: Identifier record_id	Variable name	Variable label	Variable level	Nominal values
implantation	proc_multi	Implantation procedure is	nominal	Initial BioMonitor implantation BioMonitor exchange
implantation	imp_date	Date of implantation	date	n.a.

Data file: Identifier patient_display_id_full	Variable name	Variable label	Variable level	Nominal values
data_SAR	date_initial_implant_SAR 	Date initial BM implantation	date	n.a.
data_SAR	date_latest_implant_SAR 	Date of latest BM implantation	date	n.a.

## 6.4. Effective randomization date for the ITT analyses

### CIP chapter 8.2.1 Randomization

...

*For patients of the BioMonitor group and Control group, the randomization date is defined as the discharge from the index hospitalization.*

Time-to-first-event for the ITT analyses start at the effective randomization date.

Data file: Identifier patient_display_id_full	Variable name	Variable label	Variable level	Nominal values
discharge	discharge_date	Date of discharge from index hospitalization	date	n.a.
data_SAR	date_effrand_ITT_SAR 	Date of effective randomization for ITT analysis (discharge from index hospitalization)	date	n.a.

## 6.5. Effective randomization date for the PP analyses

### CIP chapter 11.1.3 Per-protocol Analysis Set

...

*Primary endpoints are not taken into account in the BioMonitor group and in the control group until 1 month after discharge from the index hospitalization.*

Time-to-first-event analyzes start at the effective randomization date plus 30 days.

Data file: Identifier patient_display_id_full	Variable name	Variable label	Variable level	Nominal values
discharge	discharge_date	Date of discharge from index hospitalization	date	n.a.
data_SAR	date_effrand_PP_SAR 	Date of effective randomization for PP analysis (discharge from index hospitalization) + 30days	date	n.a.

 The term "index hospitalisation" refers to one of the following events:

- In patients who are enrolled with an acute myocardial infarction, it is the day on which they are discharged from hospital after conclusion of the treatment for acute myocardial infarction.
- In patients who are not enrolled in the context of an acute myocardial infarction, it is they day they leave the physician who enrolled them, with or without implanted device. It is acknowledged that this is not necessarily an overnight hospitalisation but may be a short visit only.

## 6.6. Final date for the interim ITT analyses (NOTE: Not relevant for the final analysis)

### 1st interim analysis

The latest date after index-hospitalization with confirmed information about AEs (see chapter 5.5) is used for censoring for the interim ITT analysis if there is no previous primary endpoint.

Data file: Identifier record_id	Variable name	Variable label	Variable level	Nominal values
general_notification	contact_date	Date of patient contact	date	n.a.
general_notification	visit_date	Date of patient visit in investigational site	date	n.a.
arrhythmia_notification	contact_date	Date of patient visit in investigational site	date	n.a.
arrhythmia_notification	visit_date	Date of patient visit in investigational site	date	n.a.
who_five_well_being_index	interview_date	Date questionnaire performed	date	n.a.
eq_5d_5l_questionnaire	EQ5D5L_interview_date	Date questionnaire performed	date	n.a.
adverse_events	onset_date	Onset date	date	n.a.
adverse_events	sae_date	Date AE became serious	date	n.a.
adverse_events	end_date	End date of AE	date	n.a.
adverse_events	actionhospstart_date	Start date of hospitalization	date	n.a.
adverse_events	actionhospend_date	End date of hospitalization	date	n.a.
Data file: Identifier patient_display_id_full	Variable name	Variable label	Variable level	Nominal values
discharge	discharge_date	Date of discharge from index hospitalization	date	n.a.
study_termination	term_date	Date of study termination	date	n.a.
data_SAR	date_final_1interim_SAR 	Final date with confirmed information at or after discharge about AEs for the 1st interim analysis (censoring date if there is no previous primary endpoint)	date	n.a.

## 6.7. Final date for the final PP analyses

### CIP chapter 11.1.3 Per-protocol Analysis Set

...

*Time-to-first-event data are censored after occurrence of*

- *Cross-overs from the BioMonitor group to the control group or vice versa*
- *Major protocol violations as defined in section 14.1*
- ...

### CIP chapter 14.1 CIP compliance and exceptions

... A deviation is any failure to follow, intentionally or unintentionally, the requirements of the CIP, including laws, guidelines and other regulation as far as required by the CIP, as well as applicable amendments. Deviations that are likely to seriously affect or that actually have seriously affected the rights or safety or wellbeing of subjects or the scientific integrity of the clinical investigation are major deviations (in the U.S. the term "violation" will be used). Otherwise they are minor deviations (in the U.S. simply referred to as "deviations").

The first major protocol violation will be used for censoring for the per-protocol analysis when there is no previous primary endpoint:

- Date of initial implantation in patients randomized to the control group.
- Date of "elective replacement indicator" (ERI) reported on an Arrhythmia Notification CRF, in patients randomized to the BioMonitor group if they do not receive a new device.
- First date of other major protocol violations after the effective randomization date. Major protocol deviations are documented in the CDMS file deviation\_form\_site. None of the events reported here were found to be relevant here except violation of in- an exclusion criteria and cross-overs contrary to randomization. However, these cases will be identified by other procedures defined here and this CRF doesn't have to be considered.

---

 Note: A patient with implantation before effective randomization PP is not included in the PP analysis set. Thus, the initial implantation date defined here is implicitly defined as implantation after effective randomization PP.

Data file: Identifier	Variable name	Variable label	Variable level	Nominal values
record_id				
eri_form	expl_date	Date of explantation	Date	Yes / No
arrythmia_notification	reason_multi	Reason for assessment	nominal	Arrhythmia/Event notification ERI notification ...
arrythmia_notification	helpvar_dateFormCreated		date	n.a.

Data file: Identifier	Variable name	Variable label	Variable level	Nominal values
patient_display_id_full				
study_termination	term_date	Date of study termination	date	n.a.
data_SAR	date_final_PP_SAR 	Date of first major protocol violation after the effective randomization date of the PP analysis or termination date (censoring date for PP analysis when there is no previous primary endpoint)	date	n.a.

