#### **4.6 Description of the investigational device**

The BioMonitor is a subcutaneous ICM that continuously monitors the heart rhythm. Implantation and follow-up are performed with a portable BIOTRONIK programmer. Additionally, the Home Monitoring feature enables physicians to perform remote diagnosis management over the lifetime of the device. The average service time of the BioMonitor is 4 years according to the technical manual.

The BioMonitor records automatically the occurrence of certain cardiac arrhythmias; these arrhythmias are classified as AF, high ventricular rate (HVR), asystole, or bradycardia.

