## 8 DESIGN OF THE CLINICAL INVESTIGATION

### 8.1 General considerations

The BIO|GUARD-MI study is a multicenter, prospective, randomized (1:1), controlled, parallel-group, open, international study (including USA) with an event-driven design. The study is operatively divided into 2 phases. In the first phase 640 patients will be enrolled within approximately 2 years after FPI. After 600 patient years of cumulative follow-up have been collected, a blinded analysis will be performed to assess the primary endpoint rate. Based on the assessed rate (see section 11.7), the study will enter the second phase or be discontinued prematurely. This is necessary because it is impossible to obtain solid estimates of the endpoint rates for the included population from the literature. In case of a too low endpoint rate, the study could be expected to fail in its primary objective, even if the BioMonitor group had a much reduced endpoint rate.

In the second phase enrollment will continue in the same way, but in more investigational sites than the first phase, and without interception until up to 2900 patients entered the study. The duration of the second study phase is estimated to last 4 years but ultimately is dependent on when the number of needed endpoints for the final analysis is reached. In the second phase US patients will contribute to the study.

As a result of the specific national requirements in the U.S., a U.S.-specific amended protocol is valid for U.S. sites. Differences compared to this Clinical Investigation Plan are displayed in section 23.1.

The study includes an enrollment-assessment and randomization procedure. The randomization is 1:1, either in the BioMonitor group (patients are implanted with the BioMonitor) or in the control group (patients do not receive a device). The qualifying measurement of the LVEF should be from the time after conclusion of the acute treatment of the most recent MI but not older than 6 months. For patients randomized to the BioMonitor group, the implantation shall be performed as soon as possible but at latest 8 weeks after enrollment. Most study procedures will typically take place during the index hospitalization (enrollment, implantation if applicable and discharge).

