## **8.5 Device replacement or explantation**

### **8.5.1 Device replacement**

If the BioMonitor must be replaced due to battery depletion during the study, a replacement of the device is recommended because it is assumed that patient's risk for arrhythmias and endpoints is not decreasing compared to the time of enrollment. The final decision on this topic is left with the discretion of the investigator. The patient shall remain in the study, independent of the decision to replace the device or not.

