### **8.9.6 Timelines**

[figure not shown]
First Patient In (FPI): Aug 2015 (actual date of FPI)

Last Patient Out (LPO): ~ Oct 2021 Total study duration: ~ 74 months

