### 11.4 Expected drop-out rate

A drop-out of 5% of the patients per year is expected. Thereby the limited number of patients to be excluded from the analysis set (see section 11.1.2) is not considered.

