### 11.7 Termination criteria

There is a blinded evaluation of the MACE rates after the event-check, which is no interim analysis because no therapy effect is investigated.

If the total number of patients with at least one MACE in both groups is less than 20 patients per 600 patient-years at the end of the event-check phase, the study will be terminated.

Furthermore, the sponsor may decide to discontinue the study due to organizational reasons based on the observed event rates and the general feasibility of the study. Based on the recommendations of the DSMB after the first interim analysis, the study will be stopped for futility when there is a low chance for rejection of the Alternative hypothesis at the final analysis or the need for an increase of the sample size, which is refused by the sponsor.

Stopping for superiority is achieved in case the 1-sided p-value at the interim analyses is below the O'Brien Fleming significance value  $\alpha_{\text{interim1}} = 0.00025$ .

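### SAP 6.7 lets later device replacement decide whether a BioMonitor patient is censored at battery depletion, so the supportive per-protocol comparison carries a small one-arm bias, probably but not certainly towards the device

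*SAP*

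**What the plan says.** SAP 6.7 sets the per-protocol censoring date: "The first major protocol violation will be used for censoring for the per-protocol analysis when there is no previous primary endpoint". One of the listed violations is the ERI date "reported on an Arrhythmia Notification CRF, in patients randomized to the BioMonitor group if they do not receive a new device". The section gives no time limit for the new device and no counterpart for controls.

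Protocol 8.5.1 recommends replacement after battery depletion but does not require it: "The final decision on this topic is left with the discretion of the investigator". The patient stays in the study either way. Protocol 4.6 says when depletion is to be expected: "The average service time of the BioMonitor is 4 years according to the technical manual". Protocol 8.9.6 gives the time frame: "Last Patient Out (LPO): ~ Oct 2021 Total study duration: ~ 74 months".

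Protocol 11.1.3 calls the per-protocol analysis supportive, and Protocol 11.5 rests success on the full analysis set. SAP 11.6 repeats the primary test in the per-protocol set. It adds per-protocol hazard ratios only if the primary alternative hypothesis is accepted.

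**The concern.** A censoring rule should use only what is known on the censoring date. Here that date is fixed in retrospect. Three BioMonitor patients, each free of MACE at ERI, show the effect:

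- **Replaced after an uneventful wait.** Not censored at ERI. The waiting time counts as event-free, although a patient who died in the wait could not have contributed it (immortal time).
- **Cardiovascular death before replacement.** No new device is ever received. The patient is censored at ERI and the death, a MACE under Protocol 8.3.1, is removed. A non-fatal MACE that rules out replacement is treated the same way.
- **Non-fatal MACE, then replacement.** A new device was received, so the patient is not censored and the MACE counts.

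The first two cases lower the BioMonitor event rate with no device effect, and nothing similar happens in the control arm. At stake is the per-protocol result, which would be read beside a positive ITT result as support for it.

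**Working it through.** The documents give no figure for the effect of this rule, so there is none to reproduce. Its size was obtained by simulation.

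**Inputs from the documents**
- Time to ERI: 4 years (Protocol 4.6, an average, used as fixed).
- Study length: 74 months (Protocol 8.9.6).
- Drop-out: "A drop-out of 5% of the patients per year is expected" (Protocol 11.4).
- Lower MACE rate: the stopping threshold, "is less than 20 patients per 600 patient-years at the end of the event-check phase, the study will be terminated" (Protocol 11.7), so 20/600 = 3.3% per year.

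**Assumptions, not in the documents**
- Uniform accrual over 5 years and exponential MACE times.
- Upper MACE rate of 10% per year.
- Exponential wait from ERI to replacement, mean 1 to 12 months.
- Replacement planned in 80%, unless stated otherwise.

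**Method.** One million patients per setting, true hazard ratio 1. The same patients are analysed with and without the SAP 6.7 rule, and the ratio of the two event rates is reported. A value below 1 favours the device.

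**Share event-free at ERI.** With 74/12 = 6.17 years and 5-year accrual, the fraction with more than 4 years of potential follow-up is 2.17/5 = 0.433.
- At 3.3% per year: 0.433 × 0.95⁴ × exp(−4/30) = 0.31.
- At 10% per year: 0.433 × 0.95⁴ × exp(−0.4) = 0.24.

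**Results** (3.3% / 10% MACE per year)

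| MACEs in the gap that prevent replacement | Mean wait | Overall ratio | Ratio after year 4 |
|---|---|---|---|
| all | 1 month | 0.994 / 0.994 | 0.93 / 0.92 |
| all | 3 months | 0.986 / 0.987 | 0.82 / 0.81 |
| all | 12 months | 0.977 / 0.982 | 0.63 / 0.61 |
| 30% | 1 month | 0.998 / 0.999 | 0.98 / 0.98 |
| 30% | 3 months | 0.995 / 0.996 | 0.95 / 0.94 |
| 30% | 12 months | 0.993 / 0.995 | 0.88 / 0.89 |
| none | 1 to 12 months | 0.999 to 1.001 | 0.99 to 1.01 |

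The last row should be exactly 1, so its spread shows the simulation error.

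**Reverse case.** Suppose that half of the patients not planned for replacement would get a new device after a non-fatal MACE (3-month wait, 30% of MACEs preventing replacement). The overall ratio is 1.002 with replacement planned in 80% and 1.029 with 20% (1.002 and 1.023 at 10% MACE per year). After year 4 it runs from 1.02 to 2.35.

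**A rule that does not look ahead.** Censoring every BioMonitor patient at ERI gives 1.001 and 1.000 at the two MACE rates.

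**How many patients reach ERI.** This is uncertain.
- From the 2,900 ceiling: 1,450 device patients with follow-up assumed uniform from 1 to 6 years. Two fifths (580) pass year 4. With 5% drop-out and 5% or 3.3% MACE per year, 580 × exp(−0.40) = 389 and 580 × exp(−0.333) = 416, so about 390 to 420.
- From phase 1 alone: "In the first phase 640 patients will be enrolled within approximately 2 years after FPI" (Protocol 8.1), so 320 device patients. 320 × exp(−0.40) = 215 and 320 × exp(−0.333) = 229, so about 215 to 230.

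For scale, take the phase 1 pool with 80% planned for replacement and a 3-month wait. The number of MACEs in the gap is about 229 × 0.8 × 0.0333 × 0.25 = 1.5 at 3.3% per year, or 215 × 0.8 × 0.05 × 0.25 = 2.2 at 5%. Only those that prevent replacement are lost.

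**The case against.** The case for leaving the rule alone has five parts.

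- **Most MACE components are non-fatal, and replacement is recommended.** Nothing in the documents says that a MACE stops replacement. This stands. A reader might infer that every MACE before replacement is dropped, but the text removes it only if no new device ever follows. The rows with all gap MACEs preventing replacement are therefore an extreme.
- **The direction is not established.** This stands in part. Cardiovascular death always prevents replacement, which makes a bias towards the device likely. The documents do not describe how a non-fatal MACE affects the decision, and the reverse case is possible. A reader might take the rule as certain to favour the device; the documents do not support that.
- **The number at risk is easily overstated.** This stands. SAP 5.7 dates the announcement of phase 2 to June 2018, about 40 months before the targeted last patient out in October 2021. Patients enrolled after about October 2017 would not reach a 4-year ERI in the study. Protocol 11.2 also says that the trial moved to termination early. Four years is an average and actual enrolment is not given, so 215 to 230 is not exact either.
- **No decision depends on it.** This stands for pass/fail. It does not make a biased supportive estimate acceptable. Neither document plans a landmark or late-period analysis, so the ratios after year 4 show where the bias sits but are not planned outputs.
- **Censoring everyone at ERI discards follow-up from patients who were replaced as recommended.** This is a fair cost, and it is why a grace-period version is offered below.

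The footnote that derives date_final_PP_SAR (footnote 26) is not in the text available for this review, so the coded rule could not be checked.

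**Conclusion.** The point holds as a defect of the supportive per-protocol analysis. As written, SAP 6.7 conditions on the future in one arm, and no other section corrects it. Under the assumptions above and no device effect, the overall rate ratio is 0.977 to 0.999 when some or all gap MACEs prevent replacement, a shift of at most about 2.3% towards the device. It is 1.00 when MACE does not affect replacement, and 1.002 to 1.029 when MACE prompts replacement. The simulation uses event-rate ratios and a fixed 4-year battery life, so these figures give the order of magnitude and do not predict the Cox estimate.

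Two stronger readings are not supported. The primary ITT test is not affected, because it applies no censoring at ERI. Nor do the documents show that the clause was written to favour the device. SAP 1.4 says that those responsible for version 3.0 were unblinded, and the change history lists further detail on major deviations in that version. It does not say when the ERI clause entered or why. Confidence is high that the rule looks ahead, and moderate on direction and size.

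**What to change.** Replace the condition in SAP 6.7, and in the derivation of date_final_PP_SAR, with one that uses only information available at the time. Either version works:

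1. Censor all patients randomised to BioMonitor at ERI, whether or not the device is later replaced. If post-replacement time is wanted, let patients re-enter the risk set at the replacement date in start-stop format, without the gap.
2. Censor at ERI plus a fixed, pre-stated analysis grace period if no replacement has occurred by then, and count every MACE up to that date.

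Add a per-protocol sensitivity analysis without ERI censoring. This governs only how follow-up is counted and leaves the replacement decision as Protocol 8.5.1 has it.

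The cost is a one-line text change, a matching change in the derivation and one extra run. Version 1 loses a little per-protocol follow-up. Version 2 keeps some unmonitored time after ERI.
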